8.3.2 Reporting Requirements for Serious Adverse Events and Adverse Events of Special Interest

For reports of serious adverse events and adverse events of special interest, investigators should record all case details that can be gathered immediately (i.e., within 24 hours) on the Adverse Event eCRF and submit the report via the EDC system. A report will be generated and sent to the Sponsor's Safety Risk Management department by the EDC system.

In the event that the EDC system is unavailable, a paper Serious Adverse Event/Non-Serious Adverse Event of Special Interest CRF and Fax Coversheet should be completed and sent to both BMS and Sponsor immediately (i.e. within 24 hours) to this mailbox and fax (see Appendix VII).

Fondazione IRCCS Istituto Nazionale dei Tumori	[contact]
Pharmacist: Dr.ssa [name]	[contact]
Fondazione IRCCS Istituto Nazionale	[contact]
,	
dei Tumori, [name]	1 u.u. [name]

BMS [contact]	
-----------------------------	--

BMS GPV&E can send queries for follow-up information at: [contact].

8.4 Non-serious Adverse Events

A non-serious adverse event is an AE not classified as serious.

8.5 Non-serious Adverse Event Collection and Reporting

The collection of non-serious AE information should begin at initiation of study drug. All non-serious adverse events (not only those deemed to be treatment-related) should be collected continuously during the treatment period and for a minimum of 30 days following the last dose of study treatment.

Patients who have an ongoing study treatment-related adverse event upon study completion or at discontinuation from the study will be followed until the event has resolved to baseline grade, the event is assessed by the investigator as stable, new anti-cancer treatment is initiated, the patient is lost to follow-up, the patient withdraws consent, or it has been determined that study treatment or participation is not the cause of the adverse event.

Non-serious Adverse Events (AE) are to be provided to BMS in aggregate via interim or final study reports as specified in the agreement or, if a regulatory requirement [e.g., IND US trial] as part of an annual reporting requirement.

Non-serious AE information should also be collected from the start of the lead-in treatment period.

Non-serious AEs should be followed to resolution or stabilization, or reported as SAEs if they become serious. Follow-up is also required for non-serious AEs that cause interruption or discontinuation of study drug and for those present at the end of study treatment as appropriate.

8.6 Laboratory Test Result Abnormalities

All laboratory test results captured as part of the study should be recorded following institutional procedures. Test results that constitute SAEs should be documented and reported to the Sponsor as such.

The following laboratory abnormalities should be documented and reported appropriately:

- any laboratory test result that is clinically significant or meets the definition of an SAE
- any laboratory abnormality that required the participant to have study drug discontinued or interrupted
- any laboratory abnormality that required the subject to receive specific corrective therapy.

It is expected that wherever possible, the clinical rather than laboratory term would be used by the reporting investigator (e.g., anemia versus low hemoglobin value).

8.7 Pregnancy

A pregnancy report will automatically be generated and sent to Safety Risk Management. Pregnancy should not be recorded on the Adverse Event eCRF.

Pregnancies must be reported and submitted to BMS. BMS will perform due diligence follow-up using the BMS Pregnancy Form which the investigator must complete.

The investigator should discontinue study drug and counsel the patient, discussing the risks of the pregnancy and the possible effects on the fetus. Monitoring of the patient should continue until conclusion of the pregnancy. Any serious adverse events associated with the pregnancy (e.g., an event in the fetus, an event in the mother during or after the pregnancy, or a congenital anomaly/birth defect in the child) should be reported on the Adverse Event eCRF.

If, following initiation of the investigational product, it is subsequently discovered that a study participant is pregnant or may have been pregnant at the time of investigational product exposure, including during at least 5 half-lives after product administration, the investigational product will be permanently discontinued in an appropriate manner.

The investigator must immediately notify the Sponsor in accordance with SAE reporting procedures.

Protocol-required procedures for study discontinuation and follow-up must be performed on the participant.

Follow-up information regarding the course of the pregnancy, including perinatal and neonatal outcome and, where applicable, offspring information must be reported to the Sponsor via EDC. Any pregnancy that occurs in a female partner of a male study participant should be reported to the Sponsor. Information on this pregnancy will be collected on the Pregnancy Surveillance Form. In order for Sponsor or designee to collect any pregnancy surveillance information from the female partner, the female partner must sign an informed consent form for disclosure of this information.

8.8 Overdose

An overdose is defined as the accidental or intentional administration of any dose of a product that is considered both excessive and medically important. All occurrences of overdose must be reported as an SAE.

8.9 Potential Drug Induced Liver Injury (DILI)

Wherever possible, timely confirmation of initial liver-related laboratory abnormalities should occur prior to the reporting of a potential DILI event. All occurrences of potential DILIs, meeting the defined criteria, must be reported as SAEs (see Section 8.3 and Appendix VII for reporting details).

For participants with normal ALT, AST, and Total bilirubin at baseline, potential DILI is defined as:

- 1) AT (ALT or AST) elevation $> 3 \times$ upper limit of normal (ULN) AND
- 2) Total bilirubin > 2× ULN, without initial findings of cholestasis (elevated serum alkaline phosphatase), AND
- 3) No other immediately apparent possible causes of AT elevation and hyperbilirubinemia, including, but not limited to, viral hepatitis, pre-existing chronic or acute liver disease, or the administration of other drug(s) known to be hepatotoxic.

For participants with elevated AST or ALT or Total bilirubin at baseline, potential DILI is defined as:

- 1) AT (ALT or AST) elevation > 2× baseline AND 3× ULN; OR AT elevation 8 times ULN AND
- 2) Total bilirubin > 2× baseline AND >2× ULN, without initial findings of cholestasis (elevated serum alkaline phosphatase),

AND

3) No other immediately apparent possible causes of AT elevation and hyperbilirubinemia, including, but not limited to, viral hepatitis, pre-existing chronic or acute liver disease, or the administration of other drug(s) known to be hepatotoxic.

8.10 Other Safety Considerations

Any significant worsening noted during interim or final physical examinations, electrocardiograms, X-rays, and any other potential safety assessments, whether or not these procedures are required by the protocol, should also be recorded as a non-serious or serious AE, as appropriate, and reported accordingly.

9 DATA MONITORING COMMITTEE AND OTHER EXTERNAL COMMITTEES

9.1 Data Monitoring Committee

A Data Monitoring Committee (DMC) will be used to evaluate safety during the study. Safety data will be reviewed by the DMC on a periodic basis, approximately every 3 months from the date of first-patient-in. In addition, the DMC will review safety data 28 days after the inclusion of the 6th patient. Safety data, including demographics, adverse events, serious adverse events, and relevant laboratory data, will be reviewed.

The DMC will provide a recommendation as to whether the study may continue, whether amendment(s) to the protocol should be implemented, or whether the study should be stopped. The final decision will rest withthe Sponsor.

9.2 Independent Central Review of Imaging

CD-ROM copies of the CT scans performed at baseline and during treatment until disease progression according to RECIST v1.1 and ir-RECIST criteria will be collected at the Coordinating Center (U.O. Oncologia Medica 1 Fondazione IRCCS Istituto Nazionale dei Tumori) for central review.

Site should follow their local privacy practices to de-identify all subject identifying information (name, medical record number, act.) prior to submitting images to the Coordinating Center.

Independent Central Review of imaging will be performed to assess response rate, DoR and PFS according to RECIST vers 1.1 and ir-RECIST, and to evaluate the safety of the combination.

10 STATISTICAL CONSIDERATIONS

10.1 Sample size determination

This is an open-label, multicenter, single-arm Phase II trial designed to estimate the activity of TMZ in association with NIVO and IPI in MGMT silenced, MSS, advanced CRC patients who have progressed after irinotecan, oxaliplatin, fluoropyrimidines and anti-EGFR mAbs (in *RAS/BRAF* wild type tumors).

According to our previously published results, in MGMT methylated mCRC with initial clinical benefit from TMZ (CR+PR+SD at 8 weeks) the individual PFS is almost always shorter than 6 months, and therefore the median PFS falls between 16- and 24-week reassessments. Therefore, after the first 8-week CT scan reassessment, by adding NIVO and IPI to TMZ, we plan to increase the 8-month PFS rate estimated by the Kaplan-Meier Method from 5% to 20%, with an alfa-error of 0.05 and a beta-error of 0.20.

According to the Fleming single-stage design and selecting the design parameters p0 (8-months PFS rate in the null hypothesis) = 0.05*, and p1 (8-months PFS rate in the alternative hypothesis) = 0.20, respectively, a total of 27 patients will be required. Null hypothesis will be rejected if at least 4 patients will be progression-free at the 8-months reassessment.

- *A null hypothesis of 0.05 is based on the consideration that single agent TMZ does not lead to individual PFS times beyond 6 months in the refractory setting.
- **The alternative hypothesis of 0.20 is considered as a potential target of interest for further studies in this setting with the experimental treatment.

10.2 Efficacy Analyses

10.2.1 Primary Efficacy Endpoint

The primary efficacy endpoint of this study is the 8-month PFS rate, defined as the proportion of patients alive and progression-free at 8 months from enrollment in the first treatment phase.

The primary endpoint will be 8-month (8-m) PFS in the 27 patients starting the second treatment phase. PFS status and date were assessed by the Investigators in each centre; PFS was defined as the interval from the date of enrollment in the first treatment phase to the date of first objective documentation of PD or deathfrom any cause, whichever occurred first; time was censored at the date of last follow up for patients alive and without PD. PFS will be assessed with the Kaplan-Meier method and 10-month estimates will be calculated and median (95% CI) time will be calculated.

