Having read and understood the requirements and conditions of the study protocol, I agree to perform the clinical study according to the international good clinical practice principles and regulatory authority requirements for source document verification and auditing/inspection of the study. I agree to use the study material, including medication, only as specified in the protocol. I understand that any violation of the protocol may lead to early termination of the study. I agree to the following time schedule. The study will start on January 2019 and is foreseen to be completed by July 2021.

Protocol summary

TITLE: NIVOLUMAB plus IPILIMUMAB and TEMOZOLOMIDE in combination in microsatellite stable (MSS), MGMT silenced metastatic colorectal cancer (mCRC): the MAYA study

PI: [name]

PROTOCOL NUMBER: CA209-8U4

VERSION NUMBER: 2.0

Eudract Number: 2018-004299-37

TEST PRODUCT: NIVOLUMAB (NIVO); Ipilimumab (IPI); temozolomide (TMZ)

PHASE: II

INDICATION: Confirmed metastatic or inoperable adenocarcinoma of the colon and/or rectum, with centrally confirmed mismatch repair proficiency (microsatellite stable [MSS]) by multiplex polymerase chain reaction (PCR), *MGMT* promoter methylation by pyrosequencing and MGMT absent expression by immunohistochemistry.

SPONSOR: Fondazione IRCCS Istituto Nazionale dei Tumori

Background

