- 30. For women who are not post-menopausal (< 12 months of non-therapy-induced amenorrhea) or surgically sterile (absence of ovaries and/or uterus): refusal to use a highly effective contraceptive method (i.e. with a failure rate of < 1% per year such as sexual abstinence, hormonal implants, combined oral contraceptives, vasectomized partner), during the study drug administration and for at least 6 months after the last dose of study medication. Periodic abstinence [e.g., calendar, ovulation, symptothermal, postovulation methods] and withdrawal are not acceptable methods of contraception. A combination of male condom with cap, diaphragm or sponge with spermicide (double barrier methods) is not considered a highly effective birth control method. Acceptable methods of contraception may include total abstinence in cases where the lifestyle of the patient ensures compliance. A vasectomized partner is a highly effective birth control method provided the partner is the sole sexual partner of the trial participant and that the vasectomized partner has received medical assessment of the surgical success.

31. For men: refusal to use a highly effective contraceptive method (i.e. with a failure rate of < 1 % per year such as vasectomy, sexual abstinence or female partner use of hormonal implants or combined oral contraceptives) during the study drug administration and for a period of at least 6 months after the last dose of study medication. Periodic abstinence [e.g., calendar, ovulation, symptothermal, post ovulation methods] and withdrawal are not acceptable methods of contraception. A combination of male condom with either, cap, diaphragm or sponge with spermicide (double barrier methods) is not considered a highly effective birth control methods. Acceptable methods of contraception may include total abstinence in cases where the lifestyle of the patient ensures compliance. A vasectomized trial participant is a highly effective birth control method provided that the trial participant has received medical assessment of the surgical success.

Length of Study

24 months of enrolment and 12 months of follow up

End of Study

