3.1.3 Follow up

Follow-up begins when the decision to discontinue a subject from study therapy is made (no furthertreatment with study therapy).

- Subjects who discontinue treatment for reasons other than tumor progression will continue to have scheduled tumor imaging assessments (every 8 weeks +/- 1 week for the first 12 months following C1D1 and every 12 weeks thereafter) until the patient dies, experiences disease progression (investigator-assessed RECIST 1.1-defined progression), withdraws consent or until the study closes, whichever occurs first. Subjects who started a new anti-cancer therapy in the absence of disease progression should continue to be followed for progression according to the protocol schedule of response assessments unless consent is withdrawn or the patient experiences disease progression or death or until study termination, whichever occurs first.
- All adverse events will be recorded until 30 days after the last dose of study treatment, and SAEs and AESIs will be recorded until 90 days after last dose of study treatment. Ongoing adverse events thought to be related to study treatment will be followed until the event has resolved to baseline grade, the event is assessed by the investigator as stable, new anti-cancer treatment is initiated, the patient is lost to follow-up, the patient withdraws consent, or it has been determined that study treatment or participation is not the cause of the adverse event.
- Following early discontinuation or completion of the treatment period, all patients will be followed for survival and subsequent anti-cancer therapy beginning 3 months after the end of treatment visit. Survival and subsequent anti-cancer therapy follow-up information will be collected via telephone calls, patient medical records, and/or clinic visits approximately every 3 months until death, loss to follow-up, withdrawal of consent, or study termination by the Sponsor.

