10.4 Progression Free Survival as determined by Investigator per RECIST v1.1 and Ir-RECIST

PFS is defined as the time from the first dose of TMZ to time of disease progression per RECIST v1.1 and Ir-RECIST as determined by the investigator or death due to any cause on study, whichever occurs first. Patients who have not experienced disease progression and are alive at the time of analysis will be censored at the time of the last tumor assessment.

The Kaplan-Meier method will be used to estimate PFS. The 95% CIs for median PFS were computed using the Brookmeyer and Crowley method. *Patients with no post-baseline tumor assessment will be censored at the time of first dose plus 1 day.*

A patient is considered to have disease progression by ir-RECIST if either of the following conditions is met:

- a) Ir-RECIST criteria for progression were met at a tumor assessment and no subsequent tumor assessment was performed
- b) Ir-RECIST criteria for progression were met at a tumor assessment and at the subsequenttumor assessment the criteria for confirmed progression by ir-RECIST were also met

For patients who meet criterion a), the date of progression is the date of the tumor assessment that met the criteria for ir-RECIST. For patients who meet criterion b), the date of progression is the date of the tumor assessment at which the ir-RECIST criteria for progression were first met. Patients who do not meet either of the above criteria are not considered to have had disease progression by ir-RECIST.

Patients who have not experienced disease progression and are alive at the time of analysis will be censored at the time of the last tumor assessment. The Kaplan-Meier method will be used to estimate PFS. The 95% CIs for median PFS will be computed using the Brookmeyer and Crowley method. Patients with no post-baseline tumor assessment will be censored at the time of first dose plus 1 day.

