10.9 Handling of Missing Data

For objective response (per ir-RECIST or RECIST v1.1), patients without a post-baseline tumor assessment will be considered non-responders.

For DOR, data from patients who did not experience disease progression or died will be included in the analysis as censored observations on the last date that the patient was known to be progression free, defined as the date of the last tumor assessment. If no tumor assessments were performed after the date of the first occurrence of a complete or partial response, duration of objective response will be censored at the date of the first occurrence of a complete or partial response (whichever occurs first) plus 1 day.

For the analysis of PFS, data for patients without disease progression or death will be censored at the date of the last tumor assessment (or, if no tumor assessments were made after the baseline visit, at the date of first

treatment plus 1 day). Data for patients who were lost to follow-up will be censored at the last date of tumor assessment at which the patient was known to be progression free.

For the analysis of OS, patients who are still alive at the time of analysis will be censored at the time of their last study assessment (for active patients) or at the last date known alive (for patients in follow-up).

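### The primary PFS endpoint has two conflicting censoring rules and two unlinked estimators, and no rule for patients without an evaluable 8-month scan

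*Protocol*

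**What the plan says.** On censoring, section 10.2.1, which defines the primary endpoint, states that "time was censored at the date of last follow up for patients alive and without PD". Section 10.4, on investigator-assessed PFS, says that patients alive without progression "will be censored at the time of the last tumor assessment". Section 10.9 agrees with 10.4: "data for patients without disease progression or death will be censored at the date of the last tumor assessment", and it treats patients lost to follow-up in the same way. Duration of response has the same split: section 10.2.2 uses last follow-up, while 10.3 and 10.9 use the last tumour assessment.

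On the estimator, section 10.1 says "we plan to increase the 8-month PFS rate estimated by the Kaplan-Meier Method from 5% to 20" per cent, "with an alfa-error of 0.05 and a beta-error of 0.20". It then sets a Fleming single-stage rule: 27 patients, with the null hypothesis rejected if at least 4 are progression-free at the 8-month reassessment. Section 10.2.1 defines the endpoint as a proportion at 8 months from enrolment in the lead-in phase, then assesses it by Kaplan-Meier and asks for estimates at 10 months.

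On scans, section 3.1.1 schedules tumour assessments every 8 weeks, plus or minus 1 week, from Cycle 1 Day 1 of the second phase.

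**The concern.** The go/no-go decision turns on one or two patients, so each patient's status at 8 months has to follow from one rule. Here it does not.

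Under 10.2.1, a patient can stay progression-free up to a follow-up date on which no scan was done. Under 10.9, the same patient is censored at the last scan. A patient who deteriorates, stays alive and is never rescanned is then censored rather than counted as a failure. That censoring is probably informative and would favour the treatment. Appendix III says symptomatic deterioration is a reason for stopping therapy and not an objective response category, so it would not by itself be recorded as progression.

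For response rate, section 10.9 already counts patients without a post-baseline assessment as non-responders. The primary proportion has no equivalent rule. No rejection boundary is given on the Kaplan-Meier scale either, so the reported rate and the decision can point in different directions.

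**Working it through.** 1. **The plan's own figure.** Inputs from section 10.1: p0 = 0.05, p1 = 0.20, n = 27, boundary 4. Sidedness is not stated; the Fleming single-stage rule is one-sided. Exact binomial:
   - type I error = P(X ≥ 4 | 27, 0.05) = 0.0437
   - power = P(X ≥ 4 | 27, 0.20) = 0.8177
   - with n = 26 and boundary 4, power is 0.7932, so 27 is the smallest size that meets both error limits.

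   The design reproduces. The problem lies in how the count is filled in.

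2. **Where the scans fall.** Eight months = 8 × 30.4375 / 7 = 34.8 weeks from enrolment. If the second phase starts at about week 8, scans fall near weeks 16, 24, 32 and 40. With windows of 1 week either side, none is scheduled at week 34.8. Take a patient whose last scan, at week 32, shows no progression and who is contacted at week 35. Under 10.9 the patient is censored before 8 months; under 10.2.1 the patient is progression-free past 8 months. For a Kaplan-Meier estimate this matters only if someone has an event between weeks 32 and 34.8. For a count it decides whether the patient is a success.

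3. **Count against Kaplan-Meier (illustrative data).** Take 27 patients: 10 progress at week 16, 7 at week 24, 3 are censored just after week 24, 4 progress at week 32, and 3 are progression-free beyond 8 months.
   - Kaplan-Meier: (17/27) × (10/17) × (3/7) = 0.159, above 4/27 = 0.148
   - count: 3 of 27 = 0.111, null not rejected.

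   If the three censored patients had instead progressed by week 32, both readings would give 0.111.

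4. **Worst case for the count.** Suppose k patients without a current scan are credited as progression-free whatever their true status. The type I error is then P(X ≥ 4 − k | 27 − k, 0.05):
   - k = 0: 0.0437
   - k = 1: 0.1386
   - k = 2: 0.3576.

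   The protocol gives no frequency for such patients, so k is an assumption.

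5. **After the fix.** If k patients without an evaluable scan count as failures, the tail is P(X ≥ 4 | 27 − k, p):
   - k = 1: type I error 0.0387, power 0.793
   - k = 2: type I error 0.0341, power 0.766.

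   The type I error never exceeds 0.0437, so 27 patients and boundary 4 stand.

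**The case against.** The strongest reply is that the plan, read as a whole, already ties success to a scan. The boundary is in section 10.1, not 10.2.1, and refers to a reassessment, a term that section also uses for CT evaluations. All 27 patients have had a lead-in CT without progression. Section 3.1.3 requires patients who stop treatment without progression to go on being scanned. Its telephone provision ("follow-up information will be collected via telephone calls, patient medical records, and/or clinic visits approximately every 3 months") concerns survival and subsequent therapy, so success on a telephone contact alone would need a departure from the schedule. All of this stands. A reader might infer from 10.2.1 alone that the boundary can be crossed without scan evidence; the plan as a whole does not support that. What the reply leaves open is which scan constitutes the 8-month reassessment, and what happens to a patient without one.

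A reader might also add the two upward biases together. They belong to alternative rules and cannot both apply to one patient in one analysis. Under 10.9 death is still an event, and Appendix III asks for every effort to document progression after symptomatic deterioration.

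Finally, a reader might infer that the timetable forces censoring. The investigator agreement says "The study will start on January 2019 and is foreseen to be completed by July 2021", and the synopsis allows "24 months of enrolment and 12 months of follow up". January 2019 plus 24 months plus 8 months is September 2021, past July 2021. But section 3.2 places the end of study about 12 months after the last enrolment, so every patient can reach 8 months. The July 2021 date is an administrative inconsistency.

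**Conclusion.** The point holds as a contradiction within the protocol on its primary endpoint. Sections 10.2.1 and 10.2.2 censor PFS and duration of response at last follow-up; 10.3, 10.4 and 10.9 use the last tumour assessment. A Kaplan-Meier rate and a head count are both in play and are not linked, patients without an evaluable 8-month scan have no assigned status, and the 10-month estimates do not match the endpoint.

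The sample size and boundary are right. The rise in type I error from 0.044 to 0.139 is a worst case: it assumes one patient without a current scan is counted as a success regardless of true status. It is not an expected effect. The Kaplan-Meier example shows that the estimate and the count can diverge. It does not show a changed decision, because the only stated rule is the count. Because the decision rests on so few patients, the wording should be settled before the primary analysis.

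**What to change.** - Make the exact binomial count over all 27 patients the primary analysis, with the boundary of 4 unchanged.
- Define the scan window that constitutes the 8-month reassessment, stating how the scans near weeks 32 and 40 are treated.
- Count as progression-free only patients alive, without progression, and with an evaluable scan showing this in or after that window. Count everyone else as not progression-free.
- Replace last follow-up with last evaluable tumour assessment in the PFS and duration-of-response definitions of 10.2.1 and 10.2.2, in line with 10.3, 10.4 and 10.9.
- Keep Kaplan-Meier as a supportive analysis and say so in 10.1 and 10.2.1.
- Change the 10-month estimates in 10.2.1 to match the 8-month endpoint.
- Separately, reconcile the July 2021 completion date with the enrolment and follow-up periods.

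A 90% exact interval would agree with the one-sided rule (for 4 of 27 it is 5.2% to 30.8%, whereas the 95% interval of 4.2% to 33.7% includes 5%), but it is optional.

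The cost is wording only. The observed rate may be slightly lower because missing status counts as failure, and with one or two such patients power falls from 0.82 to 0.79 or 0.77.
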